5.4 DEMOGRAPHIC AND BASELINE CHARACTERISTICS

Demographic and baseline characteristics will be summarized for all participants and by treatment arm. Characteristics to be examined include age, gender, race/ethnicity, performance status, primary disease, primary disease status, disease risk index (DRI), time from steroid initiation to enrollment, aGVHD grade and organ staging, graft source, GVHD prophylaxis, conditioning regimen, time from disease diagnosis to transplant, time from transplant to enrollment, time from aGVHD onset to enrollment, and EASIX score.

Counts and percentages will be used to describe categorical variables, while the median, mean, standard deviation, and range will be used to summarize continuous variables.

5.5 ANALYSIS OF PRIMARY ENDPOINT

The primary endpoint of this trial is the attainment of a CR at Day 28 post-randomization. The primary hypothesis is that the proportion of participants with a CR at Day 28, called the Day 28 CR rate, is greater for the T-Guard arm compared to the ruxolitinib arm. This hypothesis will be evaluated by comparing the null hypothesis that the Day 28 CR rate under T-Guard treatment is no better than this rate under ruxolitinib treatment to the alternative hypothesis that this rate is superior for the T-Guard arm.

The estimand for Day 28 CR is based on the composite strategy, where a participant is classified as a CR provided three conditions are satisfied:

1. Stage 0 aGVHD in target organs at Day 28
2. The participant is still alive at Day 28
3. No additional systemic treatment for aGVHD has been administered through Day 28

Participants who do not satisfy all three criteria will be classified as failures for CR.

The following intercurrent events could potentially impact the pivotal analysis: discontinuation of study drug before Day 28, and missingness of the Day 28 GVHD assessment. The pivotal analysis accounts for these events as follows:

- Discontinuation of study drug will be carefully monitored. Under the ITT principle, the analysis includes all randomized participants, so treatment discontinuation itself has no effect on the analysis because it produces no changes to the participant population or evaluation of CR criteria. Initiation of additional systemic aGVHD treatment following discontinuation would be considered a failure for CR per the composite strategy described above.
- Participants whose Day 28 GVHD assessment is missing for any reason (including loss to follow-up, withdrawal from study, or a missed visit) will be classified as failures (non-CRs) for the primary endpoint.

The pivotal analysis for this study involves comparison of the Day 28 CR rate between arms in the primary (ITT) analysis population. The summary measure used to compare Day 28 CR rates between T-Guard and Ruxolitinib is the odds ratio, to be evaluated using logistic regression while adjusting for region (US vs. Europe) and age (at least 55 years vs. under 55) and acute GVHD grade at randomization (Grade III vs. IV). Testing will be one-sided at an overall significance level of 0.025. Two efficacy analyses for the primary endpoint will be performed as described in Section 5.2.2, one interim and one final, with the O'Brien-Fleming error spending function used to determine the appropriate critical values for each analysis.

The Day 28 CR rate will be described for each arm using the sample proportions and corresponding 95% confidence intervals.

A secondary analysis will assess the proportions of treated participants who attain a CR at Day 28 post-treatment initiation. This set of participants will include those from the PP population who are not in CR at the time of treatment initiation, with symptoms compared from the time of initiation to 28 days following initiation to determine CR status. This Day 28 CR rate will be described for each arm using the sample proportions and corresponding 95% confidence intervals. Day 28 CR rates will be compared between T-Guard and ruxolitinib using logistic regression while adjusting for region (US vs. Europe) and age (at least 55 years vs. under 55) and acute GVHD grade at randomization (Grade III vs. IV).

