Despite recent advances in the understanding of transplantation immune pathology, aGVHD is a frequent and major complication of allo-HSCT involving activation of donor T-lymphocytes, which ultimately causes host tissue damage (Holtan SG 2014, Hill 2018, Zeiser and Blazar 2017). Serious infections, organ failure and impairment of generalized immune function are responsible for aGVHD mortality. The condition involves three target organs, the skin (presenting as inflammatory, maculopapular, erythematous rash), the liver (presenting as hyperbilirubinemia due to cholestatic jaundice) and the gastro-intestinal (GI) tract (presenting as upper and/or lower GI tract manifestations: anorexia with weight loss, nausea, vomiting, diarrhea, severe pain, GI bleeding and/or ileus) (Schoemans, Lee et al. 2018). The diagnosis must occur in absence of cGVHD symptoms (Filipovich, Weisdorf et al. 2005, Jagasia, Greinix et al. 2015). Despite immune suppression prophylaxis, up to 50% of hematopoietic cell transplantation (HCT) recipients will experience grade II-IV aGVHD (Zakias PD 2014, Zeiser, Socie et al. 2016).

Complete responses (CR) to upfront treatment at day 28 of therapy have been reported in 25% to 41% of patients, as defined as the absence of skin rash, diarrhea and hyperbilirubinemia (Hings, Severson et al. 1994, MacMillan, Weisdorf et al. 2002, Deeg 2007). With regards to second-line treatment, data from the prospective ruxolitinib treatment trials (REACH1 and REACH2), as well as from a prospective natural history trial (MAGIC), found the expected CR rate at day 28 after second-line therapy therapy is in the range of 25%-30%. The likelihood of GVHD treatment response decreases with increasing severity of the disease. (Martin, Schoch et al. 1990, Weisdorf, Haake et al. 1990). The response, more particular: Complete Response, to therapy is of central importance, as responses correlate with post-HCT survival.

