5.2.1.2 Efficacy Analysis Toward FDA Approval (Stage 2)

An analysis of the T-Guard CR rate will be performed toward obtaining FDA approval once 150 participants (75 per arm) complete the Day 28 assessments and 100 participants have completed the Day 180 assessment. This analysis will consider the CR rate specifically in the 75 participants in the T-Guard arm and will compare this to historical therapies using the second stage of the Simon's design (see [Table 5-1](#)). If 23 or more CRs are observed in this set (30.7% or higher), this will provide evidence of superiority of T-Guard in comparison to historical therapies and will support a request for FDA regular approval. Point and interval estimates of the T-Guard CR rate will be provided for this analysis using the minimum variance unbiased estimator and stagewise ordering confidence intervals proposed in Koyama et al. 2008. The additional requirement of 100 participants with 180 days of follow-up will ensure that sufficient data are available for a safety analysis that would be provided with the application for FDA approval.

5.2.2 Efficacy Analysis for Demonstrating Superiority of T-Guard to Ruxolitinib Toward EMA Approval

An interim analysis for efficacy will be conducted once 150 participants (75 per arm) complete the Day 28 assessments and 100 participants have completed the Day 180 assessment. This analysis will compare the Day 28 CR rates between trial arms (T-Guard vs. ruxolitinib) using logistic regression while adjusting for the stratification factors. An error spending approach will be employed to control the overall type I error rate using the O'Brien-Fleming spending function. Operating characteristics for this design are shown in [Table 5-2](#). This analysis in 150 participants will correspond to a one-sided significance level of approximately 0.44% as shown in the table. If superiority is not found at this analysis, a final analysis will follow once all 246 participants have completed the Day 28 assessment, at which the remaining type I error rate will be spent. A finding of efficacy for T-Guard at either this interim or final analysis will be used to support an application for EMA approval.

Table 5-2: Operating Characteristics for Trial Design

Efficacy Analysis	Sample Size	Information Fraction	Efficacy Boundary		Cumulative Type I Error Rate	Cumulative Power Under Alternative
			Difference in CR Rates	Z Statistic		
1	150	61.0%	20.19%	2.6562	0.44%	34.14%

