5.6.1 Overall Survival (OS)

OS is defined as survival of death from any cause. The time from randomization until death from any cause will be described for each arm using the Kaplan-Meier estimator. Estimates and 95% CIs for OS will be provided at Days 60, 90 and 180 post-randomization for each arm.

Provided that the pivotal analysis demonstrates superiority of T-Guard to ruxolitinib, a Cox proportional hazards model will compare the overall mortality hazard rates between the T-Guard and ruxolitinib arms through Day 180 while adjusting for the stratification factors and for acute GVHD grade at randomization (Grade III vs. IV).

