5.8.5 GVHD-related Biomarkers

Using the biomarker risk model from Major-Monfried, Renteria et al. 2018, the serum levels of GVHD-related biomarkers including REG3 α and ST2 and the 3-IS urine levels at enrollment and Day 6, 14, and 28 post-randomization will be used to estimate NRM probabilities for each participant at Day 180 following each assessment time point. The proportions of participants with high risk (defined as an estimated NRM greater than 0.29) will be described at each assessment time by treatment arm.

Moreover, the proportions of participants within each treatment arm experiencing a Day 28 CR will be described separately for participants with high risk vs. not at enrollment within each treatment arm using sample proportions and 95% Wilson score or Clopper-Pearson CIs, as appropriate. A logistic regression model will evaluate the prognostic value of biomarker risk (high vs. not) on the chance of attaining a Day 28 CR while adjusting for treatment arm.

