5.8.8 EASIX Score

EASIX score at enrollment will be summarized by treatment arm using descriptive statistics. The proportion of participants with high EASIX OS risk (defined as an EASIX score greater than 3.43) and high EASIX NRM risk (EASIX score greater than 3.61) at the time of enrollment will also be described for each arm, the risk classifications proposed in Luft et al. 2017.

Validation of these EASIX risk categories will be performed in the context of SR-aGVHD treatment considered in the current trial. OS and NRM at Day 180 post-randomization will be estimated for each EASIX risk group (high vs. not) by treatment arm using the Kaplan-Meier and Aalen-Johansen estimators, respectively. A Cox proportional hazards model will evaluate the prognostic value of EASIX OS risk (high vs. not) on the hazard rate of overall mortality while adjusting for treatment arm and a EASIX risk-treatment arm interaction term to permit possible differential effects of the treatments based on EASIX classification. A similar Cox model of the cause-specific hazard rate of NRM will evaluate the prognostic value of EASIX NRM risk (high vs. not) while adjusting for treatment arm and a EASIX risk-treatment arm interaction term.

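### The CR and OS models adjust for region, age group and Grade III/IV but leave out organ stage and screening EASIX, a modest loss of efficiency that could be avoided

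*Combined protocol and SAP*

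**What the plan says.** - **CR model.** Section 5.5 fits a logistic regression "while adjusting for region (US vs. Europe) and age (at least 55 years vs. under 55"; a third term, for baseline Grade III or IV, is also in the model. Section 5.1.4 gives the same list. Section 5.2.2, which governs the interim and final comparisons with ruxolitinib, says only "using logistic regression while adjusting for the stratification factors", and 5.1.5 likewise names only the stratification factors. The stratification factors are region and age group (5.1.2), so grade is not one of them.
- **OS model.** Section 5.6.1 fits a Cox model "while adjusting for the stratification factors and for acute GVHD grade at randomization (Grade III vs. IV". Sections 5.6.6 (non-relapse mortality) and 5.6.7 (relapse-free survival) use the same covariates.
- **Severity.** Section 1.1 states: "The likelihood of GVHD treatment response decreases with increasing severity of the disease".
- **Baseline data.** Section 4.3.2 requires acute GVHD staging, platelets, creatinine and LDH within 24 to 72 hours before enrollment, and randomization takes place at enrollment. Section 5.4 lists organ staging and EASIX as baseline characteristics to summarize.
- **Exploratory use.** Section 5.8.5: "A logistic regression model will evaluate the prognostic value of biomarker risk (high vs. not) on the chance of attaining a Day 28 CR". Section 5.8.8: "A Cox proportional hazards model will evaluate the prognostic value of EASIX OS risk (high vs. not) on the hazard rate of overall mortality". Section 5.8.8 also says the EASIX risk categories are to be validated in this setting.

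**The concern.** In logistic and Cox models, leaving out a baseline variable that predicts outcome pulls the estimated treatment effect towards no effect and costs some power, even under perfect randomization. Section 5.1.5 accepts the principle: it calls 80% conservative because the model adjusts.

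Grade III vs. IV is a coarse severity measure. Under Appendix C, Grade III covers stage 2 or 3 in liver and/or lower GI. A participant with stage 2 lower GI disease alone and one with stage 3 in both organs therefore enter the model identically.

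For survival, section 1.3.1.2.4 singles out LDH at enrollment when comparing 9 early deaths with 26 patients who lived beyond Day 30. EASIX is taken here to be built from LDH, creatinine and platelets. That is an assumption, because the plan does not print the formula.

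The stakes are a primary test with about 80% power, and OS, the only alpha-protected secondary comparison (5.6), for which no power is stated.

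**Working it through.** **1. The plan's own power figure.** Inputs (5.1.5): 43% vs. 26%, one-sided 2.5%, 80% power. The mean rate is 0.345.

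n per arm = [1.960·√(2·0.345·0.655) + 0.842·√(0.43·0.57 + 0.26·0.74)]² / 0.17² = (1.318 + 0.557)² / 0.0289 ≈ 122.

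At 123 per arm: (0.17·√123 − 1.318)/0.661 = 0.858, which is power of 80.5%.

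Two looks were then simulated with the Table 5-2 boundaries (Z = 2.6562 and 1.9817) and the futility rule (4 or fewer CRs in 23).

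| | Interim power | Final power | Type I error |
|---|---|---|---|
| Table 5-2 | 34.14% | 80.56% | 2.37% |
| Unpooled Z | 34.0% | 80.4% | 2.40% |
| Pooled Z | 32.3% | 80.0% | 2.26% |

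The stated figure reproduces with no extra covariates.

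**2. CR with added covariates.** Same looks and futility rule, 12,000 trials per row, simulation error about 0.35 points. Two independent terms were added to the planned model: one binary, and one continuous per standard deviation (SD). Assumptions not in the documents: half aged 55 or over, half US, 40% Grade IV, odds ratios of 0.8 for age, 1.0 for region and 0.5 for grade.

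| Added terms (odds ratios) | Planned | With terms | Gain |
|---|---|---|---|
| 1.0 and 1.0 | 80.9% | 80.9% | 0.0 |
| 0.7 and 0.85 | 81.0% | 81.3% | 0.3 |
| 0.5 and 0.7 | 81.2% | 82.5% | 1.3 |
| 0.3 and 0.55 | 80.2% | 85.0% | 4.8 |

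Type I error in the third scenario, at a common 26%, was 2.1% under both models.

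These terms stand for generic covariates independent of grade. Organ stage is not independent, because grade is derived from it. A separate run built grade from GI and liver stage and added linear stage terms plus a continuous biomarker (3,000 trials, no futility rule, error about 0.7 points). It gave 80.7 vs. 81.2%, 82.5 vs. 82.1% and 82.2 vs. 83.2% for no, weak and moderate added prognosis. No run tested the two stage terms alone.

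**3. OS with added EASIX.** The plan gives no OS power or target, so Day 180 OS of 60% vs. 48.7% (1.3.1.2.4) is an assumption. Under proportional hazards, HR = ln 0.60 / ln 0.487 = 0.511/0.719 = 0.71. Expected deaths are 123·0.40 + 123·0.513 = 112. Then √(112/4)·|ln 0.71| ≈ 1.81, and 1.81 − 1.96 ≈ −0.15, which is power of about 44%. Simulated Cox models (N = 246, error about 1.3 points) gave:

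| EASIX log-HR per SD | Planned | With EASIX | Difference |
|---|---|---|---|
| 0 | 42.9% | 42.1% | −0.8 |
| 0.2 | 45.4% | 47.3% | 1.9 |
| 0.4 | 45.2% | 48.7% | 3.5 |
| 0.6 | 43.6% | 51.6% | 8.0 |

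A second simulation used EASIX as high or not (37% high, 2,000 trials per row). At hazard ratios of 1, 1.5, 2 and 3 the gains were 0.1, 0.6, 3.0 and 7.2 points.

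The −0.8 lies within simulation error. As a rough check, a useless covariate costs about one death's worth of information: 1.81·√(1 − 1/112) ≈ 1.80, or about 0.3 points of power.

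**4. What the documents say about prognostic strength.** Section 1.3.1.2.4 reports 67% vs. 27% for LDH of 290 or higher. Read as 6 of 9 early deaths and 7 of 26 survivors, the odds ratio is (6·19)/(3·7) = 5.4, with Fisher p = 0.0505. This is small, post hoc and one reading of an ambiguous sentence. It supports the direction and does not fix a row in either table.

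**The case against.** The strongest reply is that this is a preference, and that the plan's choice is legitimate. Several parts of it stand.

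- A reader might infer that the models ignore baseline severity. They do not. Grade at randomization is in both, so section 1.1 is already acted on, and only a finer coding is missing.
- A reader might infer that the plan itself expects EASIX and biomarker risk to predict these outcomes. The documents do not go that far. Section 5.8.5 sets out to evaluate biomarker risk for CR, and 5.8.8 to validate the EASIX categories. Adjustment needs no validated cut-point, however, and a continuous term uses none.
- The biomarker-predicted NRM probability does not belong in the pivotal model. Baseline samples need only precede the first dose (4.3.2, Appendix B), which may come up to 72 hours after open-label randomization. The ITT population includes participants never treated, so missing samples could depend on arm. REG3α and ST2 are also assayed at different laboratories in the US and Europe.
- The OS inputs are loose. The 60% comes from 35 T-Guard patients, only 30 of whom can be Grade III-IV (5.1.5). The 48.7% is for REACH2 as a whole, where 101 of 154 ruxolitinib patients were Grade III-IV.

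What the reply does not remove is that staging and the screening laboratory values are taken before assignment, are required of everyone, and cost almost nothing to use.

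**Conclusion.** The point holds as a modest, optional gain in efficiency. Power for CR would rise by about 0 to 5 points. The upper end needs strong covariates independent of grade, so stage terms probably sit near the low end. Power for OS would rise by about 0 to 8 points, given Day 180 OS of 60% vs. 48.7%. All prognostic strengths are assumptions.

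A reader might infer that the CR test is biased or that the 80% power is overstated. Neither follows: the stated power reproduces, and type I error is unchanged. Extra covariates change which conditional odds ratio or hazard ratio is estimated, and do not correct an error. Nor can OS be said to miss a planned power, because none is stated.

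The one plain inconsistency is the covariate list: 5.2.2 omits grade, while 5.1.4 and 5.5 include it. That needs correcting whether or not anything is added.

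**What to change.** Before any unblinded comparison:

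1. Set one covariate list for the interim and final CR analyses, and use it in 5.1.4, 5.1.5, 5.2.2 and 5.5.
2. In 5.5 and 5.2.2, add lower GI stage and liver stage, each as a single linear term, from the last staging before randomization.
3. In 5.6.1, 5.6.6 and 5.6.7, add log2 EASIX from the screening laboratory values as a continuous term. State the EASIX formula and a rule for the rare missing value that does not use treatment arm.
4. Keep the biomarker-predicted NRM probability for a sensitivity analysis.

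The cost is SAP wording, a slightly longer model and a different conditional odds ratio and hazard ratio to report. If the covariates turn out not to be prognostic, the loss is at most a few tenths of a point of power. No new data are needed.

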5.6 ANALYSIS OF SECONDARY ENDPOINTS

The analysis of secondary endpoints will be based on the primary ITT analysis population. A supplemental analysis will also be performed in the PP population.

Key Secondary Endpoints:

The study has two key secondary endpoints: OS and DoCR. The comparison of OS between treatment arms will be alpha-protected; to protect the familywise type I error rate of 2.5%, a gatekeeping procedure will be employed where OS will be tested for superiority of T-Guard to ruxolitinib only if a significant benefit of T-Guard is found in the pivotal analysis of the primary endpoint.

5.6.1 Overall Survival (OS)

OS is defined as survival of death from any cause. The time from randomization until death from any cause will be described for each arm using the Kaplan-Meier estimator. Estimates and 95% CIs for OS will be provided at Days 60, 90 and 180 post-randomization for each arm.

Provided that the pivotal analysis demonstrates superiority of T-Guard to ruxolitinib, a Cox proportional hazards model will compare the overall mortality hazard rates between the T-Guard and ruxolitinib arms through Day 180 while adjusting for the stratification factors and for acute GVHD grade at randomization (Grade III vs. IV).

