The operating characteristics of the truncated test are shown in [Table 5-4](#). They were obtained from a simulation study that assumed uniform accrual of 12 participants to the T-Guard arm during the run-in phase. During the run-in phase, this procedure rejects the null hypothesis in favor of the alternative 4.6% of the time when the true Day 30 mortality rate is 15% and 74.5% of the time when the rate is 45%. If the true Day 30 mortality rate is 45%, the DSMB will, on average, be consulted when 4 events have been observed in 9 T-Guard arm participants. The limited size of the run-in phase permits reliable detection only of a true mortality rate in excess of 40% but provides some assurance of the safety of T-Guard before proceeding with full enrollment.

Table 5-4: Operating Characteristics of the Binary SPRT for Single Arm Day 30 Overall Mortality Monitoring During Run-in Phase

True Day 30 Mortality Rate	15%	20%	25%	30%	35%	40%	45%	50%
Probability of Early Stopping	4.6%	11.4%	21.6%	34.5%	48.6%	62.3%	74.5%	84.1%
Mean # Deaths by Day 30	1.8	2.3	2.8	3.1	3.4	3.6	3.7	3.7
Mean # T-Guard Participants Enrolled	11.8	11.6	11.2	10.8	10.2	9.5	8.8	8.2

*Operating characteristics obtained from 100,000 Monte Carlo simulations

A second monitoring rule will evaluate whether the Day 60 mortality risk post-randomization for the T-Guard arm exceeds that for the ruxolitinib arm throughout the trial. Based on historical

data from the REACH trials and MAGIC, the expected probability of Day 60 mortality in Grade 3-4 SR-aGVHD participants is 40%, while a rate of 65% is considered to be unacceptable. The presence of excess Day 60 mortality risk in the T-Guard arm evaluated using an SPRT that compares a null odds ratio of 1 for Day 60 mortality risk under T-Guard vs. ruxolitinib to an alternative value of 2.79. The alternative odds ratio of 2.79 corresponds to the increase in risk produced if the ruxolitinib rate equals 40% as expected while the T-Guard mortality rate is higher at 65%. This rule will only consider early stopping to reject the null hypothesis of equal mortality risk. An aggressive rejection boundary will be used during the run-in phase in order to provide enhanced vigilance in comparing risk between arms, determined by nominal type I and II error rates of 20.5% and 25%, respectively. Following the run-in, the rejection boundary is determined by nominal type I and II error rates of 5% and 10%.

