5.6.6 Non-relapse Mortality (NRM)

NRM is defined as death from any cause other than malignancy relapse/progression. The time from randomization until NRM will be described for each treatment arm using the Aalen-Johansen estimator, with malignancy relapse/progression treated as a competing risk. Estimates and 95% CIs of the cumulative incidence of NRM will be provided at Days 100 and 180 post-randomization. The cause-specific hazards of NRM will be compared between arms using a Cox proportional hazards model with adjustment for the stratification factors and for acute GVHD grade at randomization (Grade III vs. IV).

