5.6.7 Relapse-free Survival (RFS)

RFS is defined as being alive and free of malignancy relapse/progression. The time from randomization until malignancy relapse/progression or death will be described for each arm using the Kaplan-Meier estimator. Estimates and 95% CI for RFS at Day 180 post-randomization will be provided. A Cox proportional hazards model will compare the hazard rates of relapse/progression/mortality between the T-Guard and ruxolitinib arms with adjustment for the stratification factors and for acute GVHD grade at randomization (Grade III vs. IV).

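### Section 5.6.1 withholds the overall-mortality Cox model itself, not only the OS superiority claim, unless CR superiority is shown

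*Combined protocol and SAP*

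**What the plan says.** Section 5.6 protects the familywise error rate by ordering the tests: "OS will be tested for superiority of T-Guard to ruxolitinib only if a significant benefit of T-Guard is found in the pivotal analysis". Section 5.6.1 then states when the model is fitted: "Provided that the pivotal analysis demonstrates superiority of T-Guard to ruxolitinib, a Cox proportional hazards model will compare the overall mortality hazard rates", through Day 180, adjusted for the stratification factors and aGVHD grade.

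Without any condition on CR, the plan provides:

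- per-arm survival in 5.6.1: "Estimates and 95% CIs for OS will be provided at Days 60, 90 and 180 post-randomization for each arm";
- an NRM comparison in 5.6.6: "The cause-specific hazards of NRM will be compared between arms using a Cox proportional hazards model";
- an RFS comparison in 5.6.7: "A Cox proportional hazards model will compare the hazard rates of relapse/progression/mortality between the T-Guard and ruxolitinib arms";
- an exploratory model in 5.8.8 for the "hazard rate of overall mortality while adjusting for treatment arm and a EASIX risk-treatment arm interaction term";
- a comparative sequential rule on Day 60 mortality in 5.3.2: "This rule will only consider early stopping to reject the null hypothesis of equal mortality risk". Section 5.3 describes the monitoring rules as triggers for DSMB consultation.

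Section 5.2 places the final analysis of endpoints other than CR after all 246 participants complete 180 days.

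**The concern.** Gating a claim controls type I error. Gating the estimate controls nothing further and removes information. Read as written, a trial that does not show CR superiority produces two survival curves with separate intervals. It produces no adjusted hazard ratio and no stated upper limit on excess all-cause mortality.

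That is the situation in which a reader most needs the estimate, because there is no demonstrated response benefit to set against a possible mortality cost. Mortality is also a live question for this product. Section 1.3.1.2.4 reports that BMT CTN 1802 closed after its first three participants died within 30 days. It adds that randomization may help show whether the toxicities seen there were due to T-Guard or to the very high-risk population.

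**Working it through.** **1. Which between-arm models are gated.** Sections 5.6.1 to 5.6.12, read side by side:

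| Endpoint | Planned between-arm comparison | Conditional on CR? |
|---|---|---|
| OS (5.6.1) | Cox | Yes |
| DoCR (5.6.2) | Cox | No |
| Time to CR (5.6.3) | Cox, cause-specific | No |
| ORR (5.6.4), GVHD-free survival (5.6.8), toxicities (5.6.12) | Logistic | No |
| Response categories (5.6.5) | Chi-square or Fisher | No |
| NRM (5.6.6), cGVHD (5.6.9), relapse (5.6.10) | Cox, cause-specific | No |
| RFS (5.6.7) | Cox | No |
| Infections (5.6.11) | None planned | Not applicable |

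OS is the only one withheld.

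**2. How often the gate stays shut.** Table 5-2 gives cumulative power of 80.56% at 43% vs 26%. A simulation with the stated Z boundaries (2.6562 and 1.9817) and the futility rule of 4 or fewer CRs in 23 gives 79.8% to 80.4%, which agrees.

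- Design rates: 100 − 80.56 = 19.4% from the table, 19.6% to 20.2% by simulation; about 20%.
- Equal CR rates: Table 5-2 gives a cumulative type I error of 2.37%, so 100 − 2.37 = 97.6%.

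**3. What the monitoring rules provide.** Table 5-5 gives a 40.3% chance of triggering when Day 60 mortality is 40% on ruxolitinib and 50% on T-Guard. I rebuilt the Appendix F rule with odds ratio 2.79, 123 per arm, and boundary A = (1 − β)/α. That is 0.75/0.205 = 3.66 in the run-in and 0.90/0.05 = 18 afterwards.

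- The comparative rule alone triggers in 39.9%.
- Adding the Day 30 rule of Table 5-3 gives 40.3% to 41.7% if 20% to 30% of Day 60 deaths occur by Day 30, and 43.6% if 37.5% do. The plan does not state this share, so it is an assumption.

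The table figure is reproduced. The combined scheme misses this 10-point excess in 100 − 40.3 = 59.7% of trials. Across Table 5-5, the miss rate for a 10-point excess runs from 59.7% down to 46.6% (60% vs 70%).

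**4. What an ungated estimate would add.** With equal arms, SE(log HR) ≈ 2/√d for d deaths, so the 95% CI factor is exp(1.96 × 2/√d). Assume 50% mortality by Day 180, so d = 123. The REACH2 6-month OS of 48.7% quoted in 1.3.1.2.4 would give 246 × 0.513 = 126.

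- Factor: exp(3.92/√123) = exp(0.353) = 1.42.

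Power for a 10-point Day 180 deficit (Schoenfeld, one-sided 2.5%, 123 per arm), with HR = ln(S_T-Guard)/ln(S_rux) and deaths = 123 × [(1 − S_rux) + (1 − S_T-Guard)]:

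| OS, ruxolitinib / T-Guard (assumed) | HR | Deaths | Power | 95% CI at that HR |
|---|---|---|---|---|
| 60% / 50% | 1.36 | 111 | 36% | 0.93–1.97 |
| 48.7% / 38.7% | 1.32 | 138 | 37% | 0.95–1.84 |
| 40% / 30% | 1.31 | 160 | 41% | 0.96–1.79 |

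For Day 60 proportions of 40% and 50%, SE = √(0.24/123 + 0.25/123) = 0.063. The interval is ±12.4 points and power is 35%.

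**The case against.** The strongest reply is that mortality is compared between arms in several other ways, so little is lost. Much of this stands.

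- The Day 60 sequential rule is a between-arm comparison of overall mortality, and the 5.8.8 model contains treatment arm. A reader might infer that 5.6.1 holds the only such comparison; it does not. However, the sequential rule yields a trigger, not an estimate, and stops at Day 60. The EASIX model is exploratory, and with its interaction term the arm coefficient describes one risk group, not the whole trial.
- NRM and RFS are compared without a gate. Criterion 11 of section 2.4.2 excludes relapsed or persistent malignancy, and 1.3.1.2.3 reports no relapse deaths before Day 180 in the Phase 1/2 study, so NRM may track overall mortality closely. That rests on 20 patients. NRM treats relapse as a competing risk and RFS adds relapses to deaths, so neither is all-cause mortality.
- A crude difference with a CI can be derived from the two reported Kaplan-Meier estimates. That is true, but it is unadjusted and unplanned.

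Two stronger readings are tempting and fail. First, a reader might infer that after a CR failure the mortality conclusion rests on a rule that misses a 10-point excess about 60% of the time. The plan never gives the rule that role, and the figure belongs to the two rules combined. Removing the gate would not improve detection either: power is 35% to 41%, against about 40% for the monitoring scheme (with a 12.2% false-alarm rate at 40% in both arms).

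Second, a reader might infer that most FDA filings would lack a between-arm mortality comparison. At a 43% CR rate, Stage 2 succeeds in 98.2% of trials (exact binomial, 4/23 and 23/75) and the randomized interim in 34.14%. So in at least 98.2 − 34.1 = 64.1% of trials Stage 2 succeeds while the interim does not. That is all the figure shows. Section 5.2.1.2 says the follow-up requirement "will ensure that sufficient data are available for a safety analysis that would be provided with the application for FDA approval"; it does not list that analysis's contents and does not exclude a mortality contrast.

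**Conclusion.** The point holds in a limited form. Section 5.6.1 makes the adjusted overall-mortality model conditional on CR superiority when only the superiority claim needs to be. Followed literally, no overall all-cause hazard ratio with a CI is reported in about 20% of trials at the design rates and in about 97.6% if CR rates are equal.

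The loss is an estimate, not a safeguard. With an assumed 123 deaths, an observed HR of 1.0 would carry an upper limit of 1.42, which does not exclude the HR of 1.36 that corresponds to OS falling from 60% to 50%. The interval would state openly how much excess mortality remains possible. The 1.42 factor assumes full enrollment. After a futility stop (24.8% at a 26% CR rate, Table 5-1) the interval would be wider.

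**What to change.** In 5.6.1, separate the estimate from the claim, for example:

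*The adjusted Cox hazard ratio for overall mortality through Day 180, with its two-sided 95% CI, will be reported descriptively at the final analysis whatever the CR result; only the claim of OS superiority is subject to gatekeeping.*

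Here the final analysis means the one that 5.2 schedules after all 246 participants complete 180 days. The cost is one sentence. The model is already specified, the data are already collected, and no alpha is spent because no claim is attached.

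The sentence should not be extended to require a comparative OS hazard ratio at the 150-participant analysis. OS is an alpha-protected key secondary endpoint, and the open-label trial may still be enrolling toward 246, so circulating that result could affect conduct. Any mortality contrast at that point is better left to the DSMB and the FDA safety package, with access restricted while enrollment continues.
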